6.2 General Study Population

All consecutive patients presenting for acute ischemic stroke treatment and eligible for the study will be enrolled unless otherwise set out by the clinical site in advance of patient assessment. This could be the case where the site is unable to complete the informed consent process, or where the clinical centre is enrolling stroke patients in multiple studies and has set up a systematic method to enrol presenting patients across studies. Eligibility will be based on the inclusion and exclusion criteria.

The estimate of device success rate used above was based on early clinical in vivo experience with the EmboTrap device in an open case series of the CE-marked product across five European centers. The TICI 2b or greater rating achieved was reported by interventionalists at over 74%. It is expected that adjudication may reduce any self-reported adjudication as was the case in both the TREVO 2 and SWIFT studies [1, 2]. 68% was a conservative EmboTrap performance estimate and should ensure the study is large enough to accurately test the endpoint. It is lower than the early experience self-reported rate by 6%.

In the years since the study was initially designed, the self-reported rate of TICI for EmboTrap is generally higher. It is assumed that revascularization outcomes are marginally independent of each other such that no clinical site effect needs to be accounted for which would increase the standard error of any proportion estimate. This assumption will be assessed as described in Section 13.3. The evaluable sample of 176 in the ARISE II trial will be representative of the population of interest and the revascularization results are independent of each other.

7.1 Missing and Censored Data

An extra 30% to the required evaluable patient cohort number is included to bring the total cohort to 228. Missing data will be examined, and the reasons will be investigated and reported.

Missing data for the primary endpoint might be expected in the case of patients eligible for treatment (ITT) but receiving no treatment and thus would have no angiography during procedure from which to make a determination of mTICI. For the primary efficacy outcome, a simple sensitivity analysis of the ITT population will be carried out to assess the robustness

of the conclusions on this endpoint to missing data (see Section 10.3). No missing data is expected for the primary safety outcome and no imputation will be performed for missing data on secondary outcomes. Results measured outside the protocol prescribed time windows, will be treated as missing data.

8 *Timing of analyses*

8.1 *Interim analyses*

There are no planned interim analyses for this study.

8.2 *Final analyses*

All final analyses identified in this SAP will be performed after the last patient has completed the study. Before carrying out the analyses, the data management team is responsible for the database cleaning process to ensure the integrity of the analyses. No database may be locked or analyses completed until the SAP has been approved and the database will be locked prior to the initiation of the analysis. Key statistics and study results will be made available following database lock and prior to completion of the final Clinical Study Report (CSR).

Any post-hoc exploratory analyses completed to support planned study analyses, which were not identified in this SAP, will be documented and reported in appendices to the CSR.

9 *Analysis populations*

The primary efficacy endpoint will be examined for the following cohorts, An Intention to Treat cohort, a modified Intention To Treat cohort created to select a data set relevant to FDA lytic labelling constraints relevant at the time of study execution, a Per Protocol cohort, and a Treated Set cohort, which mirrors the protocol, and excludes any violations. The primary population for test will be the ITT.

9.1 *Intention to Treat*

Intention to Treat (ITT): Will include all patients who meet all angiographic eligibility criteria.

- The primary analysis for the primary efficacy endpoint will be performed on subjects in the ITT cohort with non-missing mTICI assessments.
- The primary safety endpoint analysis will be performed in the subset of treated subjects in the ITT cohort.
- Analyses on the secondary endpoints of Good Clinical Outcome and Neurological Deterioration will be performed in the subset of treated subjects in the ITT cohort with non-missing outcomes in whom rescue therapy was not employed.
- Analyses of other secondary endpoints will be performed in the subset of treated subjects in the ITT cohort with non-missing outcomes
- All specified subgroup analyses.

9.2 *Modified Intention to Treat*

Modified Intention to Treat (mITT): Prior to study initiation, during study design discussion, FDA indicated interest in results for patients where, if IV-tPA had been administered, it had been shown to fail prior to the introduction of the device. Neuravi considered that using this as an inclusion criterion could be potentially detrimental to the welfare of patients. Hence, it was determined that while no stipulation on waiting to confirm that IV-tPA had failed would be included in the protocol, Neuravi would remove these data after the fact so that data exclusive to patients where IV-tPA has failed or was contraindicated could be

reviewed. There was agreement that failure of IV-tPA would be defined as angiographic evidence of persistent target vessel occlusion, one hour or more after the initiation of IV-tPA therapy.

Accordingly, the mITT cohort is defined to reflect the lytic regime used in the TREVO 2 and SWIFT studies. The mITT cohort will include all patients in the ITT cohort with the exception of those patients in whom less than an hour elapsed between time of initial IV-tPA administration and last pre device use angiography image confirming continued presence of the clot. In order to provide additional context to the results observed in the ITT cohort,

- The analysis for the primary efficacy endpoint will be repeated on subjects in the mITT cohort with non-missing mTICI assessments.
- The analysis for the primary safety endpoint analysis will be repeated in the subset of treated subjects in the mITT cohort.
- Analyses on the secondary endpoints of Good Clinical Outcome and Neurological Deterioration will be repeated in the subset of treated subjects with non-missing outcomes in the mITT cohort in whom rescue therapy was not employed.
- Analyses of other secondary endpoints will be repeated in the subset of treated subjects in the mITT cohort with non-missing outcomes.

9.3 *Per Protocol*

Per Protocol (PP): Defines a cohort of subjects who meet all eligibility criteria and are treated with the Embotrap device. Patients with protocol violations will be excluded from analysis.

In order to provide additional context to the results observed in the ITT cohort,

- The analysis of the primary efficacy endpoint will be repeated on patients in the PP cohort with non-missing mTICI assessments.
- The analysis of the primary safety endpoint will be repeated on patients in the PP cohort.

9.4 *Treated Set*

Treated Set (TS): Defines a cohort of subjects who are treated with the EmboTrap device regardless of study eligibility. In order to provide additional context to the results observed in the ITT cohort,

- The analysis of the primary efficacy endpoint will be repeated on patients in the TS set with non-missing mTICI assessments.
- The analysis of the primary safety endpoint will be repeated on patients in the TS set.

10 General issues for Statistical Analysis

10.1 *Software used for the analysis*

All Primary and secondary statistical analyses will be validated by an independent statistician, or using independent software (R, SAS, SPSS, Minitab or Stata). All of the code generated will be kept by both the study statistician and the independent statistician.

10.2 *Confidence intervals*

All confidence intervals reported for binary variables will be Wilson exact binomial confidence intervals and for continuous variables will be based on a normal distribution assumption for the parameter of interest.

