10.2 Protocol deviation

Any other events that do not comply with the requirements of the protocol will be considered *protocol deviations*.

Protocol deviations include, but are not limited to, the following list:

- Incorrect version of the informed consent form used.
- Patient did not attend follow-up visit or follow-up visit was outside the required window.

All protocol violations and deviations from the study protocol must be reported to the appointed Neuravi representative/ study monitor on a protocol violation/deviation form, regardless of whether medically justifiable, pre-approved by Neuravi or taken to protect the subject in an emergency. In addition, the investigator is required to adhere to the ethics committee/IRB procedures for reporting protocol violations and deviations.

Investigators must obtain prior approval from Neuravi before initiating deviations from the investigational protocol, except in situations where necessary to protect the life or physical well-being of a subject in an emergency situation, or situations beyond the investigator's control (such as subjects not attending scheduled follow-up visits, etc.). Approval for deviations shall be documented in writing and maintained in the investigator and clinical study management files. All deviations will be reported to Neuravi, regardless of medical justification, pre-approval by Neuravi, or emergency nature. Subject-specific protocol deviations will be reported using the protocol deviation form eCRF. Non-subject-specific protocol deviations (e.g. unauthorized use of the investigational device in the US outside the study, unauthorized use of the investigational device in the US by a physician who has not signed the investigator agreement, etc.) shall be notified in writing to Neuravi. FDA regulations (21 CFR 812.140 (a) (4)) require investigators to maintain accurate, complete and current records, including documentation showing the dates of and reasons for each deviation from the protocol. Per 21 CFR 812.46 (a), failure to comply with the investigational plan may result in termination of the investigator's participation in the study.

11 Device Accountability

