The modified TICI (mTICI) result for assessing the primary efficacy endpoint for a subject will be taken from the final core laboratory adjudicated angiographic result with EmboTrap (within 3 passes).

5.2.2 **Primary Safety endpoint**

The primary safety endpoint will be measured as the confirmed occurrence of Symptomatic Intracerebral hemorrhage (sICH) within 24 hours (-8/+12 hrs) post-procedure, together with any other Serious Adverse Device Effects (excluding those already counted in sICH).

5.2.3 **Secondary endpoints**

For patients on whom rescue therapy was employed during the procedure, those secondary endpoints related to neurological outcomes observations will be removed from the data set as detailed in the protocol CIP003 rev 05 and these patients excluded from the main analysis of Good clinical outcome (mRS) and Neurological deterioration. This treatment will apply to the following secondary endpoints:

- **Good clinical outcome** – judged to be an mRS score of ≤2 at 90(+/-14) days.
- **Neurological deterioration** – defined by an increase of 4 points or more on the NIHSS score, at the 24-hour time point.

Sensitivity analysis will be performed to assess the robustness of results for these two endpoints to variations in how rescue therapy is defined to define the success of failure to reach an endpoint (Section 10.8).

For the statistical analysis of remaining secondary endpoints, rescue therapy will not be a consideration.

- **Procedure Time** – the time from groin puncture to final angiographic result.
- **Time to treat** - the time from angiographic visualization of large vessel occlusion to achievement of \geq mTICI 2b, or if not achieved, final angiogram. The number of passes to get to mTICI 2b or greater flow will also be recorded.
- **Mortality post-procedure** – All procedure-related mortality (i.e. directly traceable to a procedure- related SAE) at Day 7 post-procedure and all-cause mortality at 90(+/-7) days post-procedure.
- **Serious Adverse Device Effect (SADE)** – CEC confirmed that the EmboTrap device caused, or cannot be ruled out as having caused, an effect that has resulted in any of the consequences characteristic of a serious adverse event.
- **Procedure Related Serious Adverse Events (PRSAE)** – CEC confirmed that the interventional procedure caused, or cannot be ruled out as having caused, an effect that has resulted in any of the consequences characteristic of a serious adverse event.

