- **Symptomatic ICH (sICH)** – any extravascular blood in the brain or within the cranium associated with clinical deterioration, as defined by an increase of 4 points or more in the NIHSS score, or that leads to death and is identified as the predominant cause of the neurologic deterioration [3]. For the purpose of data analysis, subjects with sICH identified through all post-treatment scans up to the 24 hour timepoint (including those performed due to clinical deterioration), will be counted.
- **Evidence of Infarction** – Infarction of a previously uninvolved vascular territory, as evaluated from 24-hour imaging (Computed Tomography (CT)/Magnetic Resonance Imaging (MRI)) by the Angiography Core Lab.

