10.3 Methods for Withdrawals, Missing Data, and Outliers

The proportions and causes of missing data for each outcome will be reported. Due to the nature of the data, follow-up schedule and the patient cohort, it is expected that the amount of missing data in the primary and secondary endpoints will be minimal.

For the primary efficacy and outcome, a simple sensitivity of the primary ITT analysis will be carried out by imputing the proportions of success within those participants with a missing outcome (missing mTICI score). This will be done across a range of proportions from 0 to 1 in a “tipping point analysis” [3, 4] for assessing of the robustness of the conclusions on the primary endpoint to missing data. For the secondary outcomes of Good Clinical Outcome and Neurological Deterioration, best and worst case scenario analyses will be performed by treating patients with missing outcomes as successes and failures, respectively.

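### SAP 7.1 turns known out-of-window mRS and 24-hour NIHSS scores into missing data, and no planned analysis uses them

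*SAP*

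**What the plan says.** The rule comes from several sections read together.

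- **SAP 7.1:** "Results measured outside the protocol prescribed time windows, will be treated as missing data". The same section says that "no imputation will be performed for missing data on secondary outcomes". Protocol 8.2.1 had planned multiple imputation for missing endpoint data.
- **SAP 9.1:** good clinical outcome and neurological deterioration are analysed in "treated subjects in the ITT cohort with non-missing outcomes in whom rescue therapy was not employed". The other secondary endpoints also use non-missing outcomes only.
- **SAP 10.3:** for those two endpoints, "best and worst case scenario analyses will be performed by treating patients with missing outcomes as successes and failures, respectively".
- **SAP 10.8, Table 4:** the sensitivity analyses vary the handling of rescue therapy and the analysis population. None uses out-of-window values.
- **Windows:** good clinical outcome is "judged to be an mRS score of ≤2 at 90(+/-14) days" (SAP 5.2.3), that is, days 76 to 104. The 24-hour assessment runs from 16 to 36 hours (Protocol 6.5.6; SAP Table 2); SAP 5.2.2 words the same window for primary safety as "within 24 hours (-8/+12 hrs) post-procedure".
- **Status of a late visit:** Protocol 10.2 lists as a deviation, not a violation, "Patient did not attend follow-up visit or follow-up visit was outside the required window". It does not say that the result is discarded.
- **Imaging:** for sICH, SAP 5.2.3 counts "subjects with sICH identified through all post-treatment scans up to the 24 hour timepoint". Protocol 7.1 brings into the analysis any scan done because of deterioration before the routine 24-hour scan. New-territory infarction is read from the 24-hour imaging, with no such provision in its definition.

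**The concern.** The rule applies to results that were measured, so the value exists. No section distinguishes a score taken late from a score never taken. A patient whose mRS is recorded on day 106 leaves the main rate. In the sensitivity analysis the same patient counts once as a success and once as a failure, although the answer is on file.

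Two things are at stake. First, if patients seen outside the window differ from those seen inside it, the reported rate describes a selected group, and no planned analysis would reveal this. Second, the best/worst range reports uncertainty that is not there. Protocol section 4 intends the secondary endpoints for side-by-side comparison with the stent-retrievers in the SWIFT and TREVO II studies, so the 90-day rate will be read against outside figures even though it is not tested.

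**Working it through.** **The plan's own figure.** The out-of-window rule has no figure attached. The stated design reproduces: with n = 176, a goal of 0.56 and an exact one-sided test at 0.025, success needs at least 112 responders. The exact alpha is 0.0240, and power at 0.68 is 0.906. The primary efficacy endpoint is an angiographic result obtained during the procedure, so a follow-up window cannot change these numbers.

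**Set-up for good clinical outcome.** Let M be the treated, non-rescue patients with any score, k those scored out of window, x the in-window successes and y the out-of-window successes.

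- Rate reported under SAP 7.1 and 9.1: x/(M−k)
- Rate using every observed score: (x+y)/M
- Difference: (k/M) × (in-window rate − out-of-window rate)
- Planned worst and best case: x/M and (x+k)/M, a width of k/M from these patients alone

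**Assumed inputs (none is in the documents).** M = 176; out-of-window shares of 2%, 5% and 10% (k = 4, 9, 18); in-window success of 50% or 60%; out-of-window success of 30%, 50% or 80%. Counts are rounded to whole patients.

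| k of 176 | Reported rate too high by at most | Reported rate too low by at most | Added best/worst width |
|---|---|---|---|
| 4 | 0.8 points | 0.6 points | 4/176 = 2.3 points |
| 9 | 1.4 points | 1.4 points | 9/176 = 5.1 points |
| 18 | 3.3 points | 2.8 points | 18/176 = 10.2 points |

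**Worked case, k = 18.**

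- In window: 95/158 = 60.1% (Wilson 95% interval 52.3 to 67.4).
- With 5 successes among the 18 (30%, rounded): 100/176 = 56.8% (49.4 to 63.9). Difference 60.1 − 56.8 = 3.3 points.
- Planned worst case 95/176 = 54.0%; planned best case 113/176 = 64.2%. If the 18 known scores were used, these patients would add no width.
- Opposite sign: in window 79/158 = 50.0%; with 14 successes among the 18, 93/176 = 52.8%, so the reported rate is 2.8 points too low.

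**Smaller denominator.** 176 is the evaluable number for the primary endpoint, and good clinical outcome also excludes rescue patients. With M = 132 (176 × 0.75, assumed) and k = 3, 7 and 13, the largest shifts are 0.6, 1.9 and 2.8 points and the added widths are 2.3, 5.3 and 9.8 points.

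**The other endpoints.** Neurological deterioration follows the same formulas, with the 16 to 36 hour window. For new-territory infarction, a scan after 36 hours drops out of the denominator; SAP 10.3 sets no best/worst bounds for that endpoint.

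**The case against.** The strongest reply is that the ±14 days are part of the mRS endpoint definition. A uniform prespecified window follows that definition and prevents case-by-case choice of values. That stands: an in-window main analysis is defensible.

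Four stronger readings are tempting, and the documents do not support them.

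- *The best/worst analysis overwrites real scores with invented ones.* The two scenarios are bounds. Since y lies between 0 and k, the all-observed rate always falls inside them. They are wider than they need be, not wrong.
- *The good-outcome rate is biased upward because dependent patients return late.* Nothing in the documents says who returns late; recovered patients may do so too. The table shows both signs.
- *All out-of-window imaging is discarded.* sICH and early scans done for deterioration have their own provisions. What is left is mainly the late scan for new-territory infarction, and an unstated order of precedence between those provisions and SAP 7.1.
- *The observation nearest to 24 hours should simply replace the windowed one.* Without an outer limit, a day-7/discharge NIHSS could enter a 24-hour endpoint. The choice among several in-window values could also change.

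It can also be said that SAP 10.3 expects minimal missing data and reports its causes, and that SAP 11.2 reports deviations by type. The first may well make the effect small. The reporting helps only in part: the listed deviation type puts non-attendance and late attendance in one item, and a count does not show what the late scores were.

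**Conclusion.** The point holds as a gap in the sensitivity analysis and in the definition of missing. Measured mRS and 24-hour NIHSS values are treated as unknown, and no planned run uses them.

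The size cannot be fixed from the documents. It depends on the out-of-window share and on how those patients fared, and both are assumed here. Over the assumed range, the effect runs from under 1 point at 2% out of window to about 3 points at 10%. The spurious best/worst width equals the out-of-window share itself. The affected endpoints are descriptive and carry no hypothesis test, and the primary efficacy conclusion does not depend on them. This is a cheap improvement to the 90-day and 24-hour results, not a threat to the trial's main claim.

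**What to change.** 1. **SAP 10.8:** add an all-observed analysis of good clinical outcome, neurological deterioration and new-territory infarction. Use out-of-window values within an outer limit fixed in advance for each endpoint, set so that a day-7/discharge NIHSS cannot stand in for the 24-hour score. Leave the selection of in-window values unchanged. The in-window analysis may remain the main one.
2. **SAP 10.3:** apply best/worst-case scoring only to patients with no usable observation. Report the number measured out of window separately from the number never measured.
3. **SAP 7.1:** state how the window rule relates to the sICH definition in SAP 5.2.3 and to the early deterioration scans in Protocol 7.1, so that it is clear which passage governs imaging.

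The cost is SAP wording and one extra run. Visit dates are already to be taken from the eCRF under SAP 11.1. The added analysis will have slightly more spread in assessment time.

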10.3 Methods for Withdrawals, Missing Data, and Outliers

The proportions and causes of missing data for each outcome will be reported. Due to the nature of the data, follow-up schedule and the patient cohort, it is expected that the amount of missing data in the primary and secondary endpoints will be minimal.

For the primary efficacy and outcome, a simple sensitivity of the primary ITT analysis will be carried out by imputing the proportions of success within those participants with a missing outcome (missing mTICI score). This will be done across a range of proportions from 0 to 1 in a “tipping point analysis” [3, 4] for assessing of the robustness of the conclusions on the primary endpoint to missing data. For the secondary outcomes of Good Clinical Outcome and Neurological Deterioration, best and worst case scenario analyses will be performed by treating patients with missing outcomes as successes and failures, respectively.

